Seven Cigarette purchase sessions (approximately 1.5 hours). In the remaining seven cigarette purchase sessions (may be more than 7 due to factors outside of the control of participants, for example, a participant is eligible to start a purchase session but blood is unable to successfully be drawn), we will assess the behavioral economic demand intensity and elasticity of cigarettes with different nicotine concentrations. During each of these 7 cigarette purchase sessions, participants will consume either their usual brand of cigarette, an experimental cigarette containing 0.4 mg/g, 1.4 mg/g, 2.5 mg/g, 5.6 mg/g, or 17.4 mg/g nicotine, or a nonusual brand, commercially available cigarette. All but the nonusual brand, commercially available cigarettes will be presented in a randomized order across participants to control for any order effects; the nonusual brand, commercially available cigarette will be administered during the 7th session. The participants' preferred brand of conventional cigarettes will be used for the appropriate session. The cigarette doses will be blinded so the participants are not aware of the dose they will administer, leaving only subjective effects. Participants will be asked to abstain from consuming nicotine for 12 hours prior to each cigarette purchase session. Abstinence will be verified with breath CO at the beginning of the session, which will need to be <8 ppm to participate. If participants do not meet this criterion, they will be allowed to reschedule the session and try again. After repeated failed attempts, participant participation may be terminated. Each purchase session will begin with baseline ratings of nicotine craving, current drug effect, breath CO, and nicotine withdrawal symptoms. The baseline blood draw will also be collected at this time. Blood will be drawn with a catheter throughout the session by a registered nurse or other personnel with phlebotomist training to measure plasma nicotine levels during the sessions. The catheter will be removed at the end of each purchase session. Snacks and/or beverages will be available for the participants to consume, at their own discretion, should they begin to feel light-headed.

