Five minutes into the session, participants will consume the cigarette randomly chosen for that session. Consumption will be modeled after the initial consumption period of Vansickel and Eissenberg (2013) and will consist of 10 puffs with each puff initiated 30 seconds after the previous. Consumption will occur in ventilated booths located in the Addiction Recovery Research Center specifically designed for this purpose.

To measure how the subjective effects and plasma nicotine levels dissipate over the course of an hour, visual analogue scales (VAS) ratings, breath CO, and 7 blood draws (3 mL each), including the baseline one, will be collected throughout the session (baseline and at minutes 10, 15, 20, 30, 45, and 60). The catheter will be flushed with saline (1 mL) after each draw, followed by a 1 mL discard draw to remove the saline flush. No heparin will be used. The 3 mL blood drawn per draw would result in 21 mL total blood per session and 126 mL total over the six cigarette purchase sessions. To maintain sterility, the site is covered with a Tegaderm, the port is cleansed with alcohol, and the staff handle the IV site with clean, gloved hands. After the VAS ratings at one of the timepoints, participants will complete hypothetical purchase tasks for the product they just consumed and some brief discounting tasks, similar to the ones completed during the

assessment session. The value of the nicotine product just consumed will be assessed by asking how many cigarette puffs the participant would purchase if they were available at different prices. Hypothetical purchase tasks are typically used to measure the consumption of a product already familiar to the participant. In this project, we will use this procedure in a novel way by asking participants to indicate their consumption decisions for a product they just consumed, but remain blinded to the nicotine content. This will prevent their responses being biased by preconceptions of dose information, instead tying purchasing behavior to the experienced effects of each dose.

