To measure how the subjective effects and plasma nicotine levels dissipate over the course of an hour, VAS ratings and blood draws will be collected immediately after the 5-minute administration period at minute 10, and again at minutes 15, 20, 30, 45, and 60. We will use closed intravenous catheter systems to avoid multiple needle sticks per session. At minute 20 (10 min after the end of the consumption period), participants will complete a hypothetical purchase task for the cigarette they just consumed, similar to the ones completed during the assessment session (see **Table 1**). Hypothetical purchase tasks are typically used to measure the consumption of a product already familiar to the participant. In this experiment, we will use this procedure in a novel way by asking participants to indicate their consumption decisions for a product they just consumed, but remain blinded to the nicotine content. This will prevent their responses from being biased by preconceptions of dose information, instead tying purchasing behavior to the experienced effects of each dose.

Participants will be compensated \$20 for the consent session, \$40 for the assessment session, \$40 for each of the six cigarette purchase sessions, and \$75 for completing all sessions for a maximum total of \$375.

Sample Size Justification

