where Q is consumption of the commodity, C is the price, Q_0 is the derived initial consumption without cost constraints (demand intensity), k is the span of the function in logarithmic units, and α is the demand elasticity. Q and C are determined by the data and k is set to a constant determined empirically by the actual data, leaving only Q_0 (demand intensity) and α (demand elasticity) as free parameters to be fitted. Analysis will proceed by fitting the above equation to individual subject data, then comparing demand intensity and elasticity consistent with the goals of each analysis. Intensity and elasticity from the demand function will be compared among the different cigarette types with nonlinear regression, as we have done previously (e.g., Koffarnus, Hall, et al., 2011; Koffarnus, et al., 2015). Then, mixed effects models will be used to characterize intensity and elasticity as a function of cigarette type. A random effect will be included to model repeated measures on subjects, and socio-economic and other demographic variables will be statistically screened for inclusion using

model-based hypothesis tests. These analyses will allow us to detect which doses fall on the same unit price curve and which doses do not and constitute a low-dose exception that we hypothesize will be related to lack of abuse liability. Additionally, we will be able to inform regulators how cigarettes at different doses are likely to affect unrestricted consumption (demand intensity) and cigarette valuation (demand elasticity).

In addition to the demand data, we will compare the VAS measures of drug effect as a function of cigarette dose to determine if these measures coincide with demand intensity, demand elasticity, or both. For these analyses, we will use mixed effects models to compare cigarette type and dose for the VAS measures and to control for the variance associated to subject in this within-subject design.

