Participant retention may be a limitation. This study requires repeated laboratory visits with a period of nicotine abstinence preceding most visits in Experiment 1, which may be difficult for some participants to accomplish. We have experience successfully completing studies with similar lab visit requirements, and to counteract this difficulty, we have budgeted for a projected dropout rate appropriate for each experiment based on previous experiments conducted in our lab with similar visit and abstinence requirements.

Those that drop out in Experiment 1 may be more likely to be heavy smokers who find the abstinence criterion more difficult, which could bias our results. To mitigate this limitation, we will perform an analysis of participants who drop out versus those who remain enrolled to detect any demographic differences or nicotine product use pattern differences and incorporate any differences as covariates in our statistical analysis where appropriate.

Project Timetable

Over the course of the three-year grant period, Experiment 1 will be completed in year 1 and Experiment 2 will be completed in years 2 and 3. The first 2 months of Experiment 1 will be allocated toward preparing for this experiment (i.e., training staff, preparing standard operating procedures, purchasing supplies, etc.), allowing 10 months to recruit and run the estimated 58 participants needed to complete 36 participants, or an average of 5.8 participants per month. Data analysis and manuscript preparation for this experiment will be completed in year 2 concurrently with the running of Experiment 2. The first 2 months of Experiment 2 in year 2 will be allocated to preparing for this experiment, with the final 2 months of year 3 allocated toward data analysis and manuscript preparation, leaving 20 months to recruit and run the estimated 174 participants needed to complete 150 participants, or an average of 8.7 participants per month. Over the past 12 months, studies in our laboratory with cigarette smokers as participants maintained an average of 30.8 participants enrolled per month. This far exceeds our requirements for the proposed enrollment goals for the proposed Experiment 1 (5.8 per month) and Experiment 2 (8.7 per month), assuring that we will be able to obtain the requisite number of eligible participants.

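### Experiment 1 rates craving, drug effect and withdrawal before smoking at every session, but the planned VAS and demand models leave session-to-session variation in that starting state in the residual

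*Combined protocol and SAP*

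**What the plan says.** **Collection.** Section 5.1 of the Experiment 1 IRB application says: "Each purchase session will begin with baseline ratings of nicotine craving, current drug effect, breath CO, and nicotine withdrawal symptoms". The same section times the VAS ratings, breath CO and blood draws as "baseline and at minutes 10, 15, 20, 30, 45, and 60". Smoking starts five minutes into the session, so the baseline values come before any effect of that session's cigarette.

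**Analysis.** In the analysis text (Experiment 1, Data Analyses, Demand Analyses by Nicotine Content), "mixed effects models will be used to characterize intensity and elasticity as a function of cigarette type". On the remaining terms: "A random effect will be included to model repeated measures on subjects", and "socio-economic and other demographic variables will be statistically screened for inclusion". For the subjective ratings, "we will use mixed effects models to compare cigarette type and dose for the VAS measures", with subject variance controlled.

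**Other covariates.** Difficulties and Limitations adds a comparison of dropouts with those who stay, to "detect any demographic differences or nicotine product use pattern differences and incorporate any differences as covariates in our statistical analysis where appropriate". These too are characteristics of the person.

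No section gives the session's pre-smoking ratings a role in the analysis, whether as covariate, change score or model timepoint.

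**The concern.** All cigarette comparisons in Experiment 1 are made within a person. The subject term removes stable differences between people. A demographic or socio-economic covariate is constant across one person's sessions, so with complete, balanced data it leaves the cigarette contrasts unchanged. The nuisance variation that matters is between sessions: a participant may arrive with more craving or withdrawal on one day than on another. The trial measures this state before every cigarette, but the models make no use of it.

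The aim is to find the dose at which demand departs from the common unit-price curve. That means separating neighbouring low doses, which is harder than the omnibus test used for sizing. The timetable also expects to enrol 58 people to obtain 36 completers, so precision from data already in hand would be useful.

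**Working it through.** **Inputs.** Sample Size Justification, Experiment 1: n = 36 completers, f = 0.175, 80% power, m = 6 repeated measures, α = 0.05. The documents do not give the correlation among repeated measures (ρ), the sphericity factor (ε) or the session-level correlation (r) between pre-smoking rating and outcome. I assume ρ = 0.5 and ε = 1, and show a range for r.

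**1. Reproduce the plan's figure.** For a one-group within-factors ANOVA, λ = f²·n·m·ε/(1 − ρ) = 0.030625 × 36 × 6/0.5 = 13.23, with 5 and 175 degrees of freedom. Power is 79.97%, so the stated 80% is reproduced (37 are needed to reach 80% strictly). The result depends on the assumptions: at n = 36, ρ = 0.3 gives 63.2%, ρ = 0.7 gives 96.5%, and ε = 0.7 (with ρ = 0.5) gives 68.3%.

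**2. Add the session baseline.** If r is the correlation between within-person deviations of the pre-smoking rating and of the outcome, adjustment multiplies the residual variance by 1 − r². Then λ becomes 13.23/(1 − r²), and one error degree of freedom is lost (174).

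| r (assumed) | 1 − r² | λ | Power at n = 36 | Completers for 80% | Detectable f at n = 36 |
|---|---|---|---|---|---|
| 0 | 1.00 | 13.23 | 80.0% | 37 | 0.1751 |
| 0.1 | 0.99 | 13.36 | 80.4% | 36 | 0.1742 |
| 0.2 | 0.96 | 13.78 | 81.8% | 35 | 0.1715 |
| 0.3 | 0.91 | 14.54 | 84.1% | 33 | 0.1670 |
| 0.5 | 0.75 | 17.64 | 91.2% | 28 | 0.1516 |

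A simulation with 4,000 runs per value of r agrees. Adjusted power was 83.8% at r = 0.3 and 91.8% at r = 0.5, against 79% to 81% unadjusted. At r = 0, adjusted power was 80.2% against 80.7% unadjusted, so a useless covariate costs almost nothing.

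**3. Compare a change score.** With equal within-person variances before and after smoking, a change score multiplies the residual variance by 2(1 − r): 2.0 at r = 0, 1.4 at r = 0.3 and 1.0 at r = 0.5. Simulated power is 46.8%, 62.6% and 79.4%. Below r = 0.5 this is worse than ignoring the baseline.

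**4. Where the figures apply.** The plan sized n = 36 and f = 0.175 for demand and states no effect size for VAS. For VAS, the table shows what a given r would buy at the plan's own effect size. For demand there is no pre-smoking value on the same scale, because the purchase task concerns the cigarette just smoked. There r would be a correlation between craving and a demand parameter, and nothing in the documents points to its size.

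**The case against.** The strongest reply is that the design already controls starting state. Section 5.1 of the IRB application asks for 12 hours without nicotine before each purchase session, checks breath CO below 8 ppm and reschedules those who fail. Pre-smoking drug effect after abstinence may also sit near the bottom of its scale and so predict little. This stands as a limit on size: r may be low, and at r of 0.2 or less the gain is under two points of power. The rules narrow variation in craving and withdrawal but do not remove it.

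It is also fair that the text does not forbid using the baseline. The analysis text's own session description starts mid-sentence and its sequence figure is not shown, so the evidence of collection comes from the IRB application. The Experiment 1 Data Analyses text appears complete, however, and names no session-level covariate.

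A reader might infer three stronger points that the documents do not support:

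- **Bias.** Six cigarettes are given in randomised order, so starting state adds noise to their comparison and does not bias it. The non-usual commercial brand is always smoked at session 7, where drift could matter, but the six-condition analysis does not name that cigarette.
- **Dilution.** If baseline were one of seven averaged VAS outcomes, a session-average effect would shrink by 1/7. The analysis text lists post-smoking times only: "VAS ratings and blood draws will be collected immediately after the 5-minute administration period at minute 10, and again at minutes 15, 20, 30, 45," with the last at minute 60. It states no model that averages over seven times.
- **A large saving in participants.** At r = 0.7, 36/(1 − 0.49) is about 71 unadjusted completers, but nothing in the documents supports so high an r.

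**Conclusion.** The concern holds as a modest point about precision. The pre-smoking ratings are collected at every purchase session, and the stated models do not use them, so session-level variation in starting state remains in the error term of the within-subject contrasts. The unadjusted comparison of the six randomised cigarettes is valid, and the plan's power figure reproduces without a baseline covariate.

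Under ρ = 0.5 and ε = 1, the gain at n = 36 and f = 0.175 runs from nothing at r = 0, through about 4 points at r = 0.3, to about 11 points at r = 0.5. All three quantities are assumptions, and the abstinence rule makes the lower end plausible. The case is better for VAS, which has a baseline on the same scale, than for demand intensity and elasticity, where craving is a different construct. The change is one to consider, with little downside.

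**What to change.** **VAS models.** State that the outcome is the ratings at minutes 10 to 60, as the analysis text lists them. Include that session's pre-smoking rating of the same scale as a pre-specified covariate, entered as two terms: the participant's mean over sessions and the session's deviation from that mean. The deviation carries the within-person gain, whereas the raw rating mixes it with stable differences between people. Say that a change score will not be used.

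**Demand intensity and elasticity models.** As a secondary option, pre-specify the session's pre-smoking craving in the same split form, outside the significance screen applied to demographic variables. Note that the gain there is less certain.

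**Cost.** A few sentences of analysis text, settled before the data are examined. There are no new measurements or visits. The session deviation costs one error degree of freedom per covariate in the within-person contrasts, and the subject mean uses one between-person parameter.

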
The four marketplace sessions (presented in a counterbalanced order) will consist of the following conditions:

1. Price of conventional cigarettes will be manipulated with other nicotine products at a constant price
2. Price of experimental cigarettes will be manipulated with no other products available
3. Price of experimental cigarettes will be manipulated with other nicotine products at a constant price
4. A blend of 1 and 3 such that price of conventional cigarettes and experimental cigarettes will be simultaneously available (one will be manipulated while the other is held constant and vice versa) with other nicotine products at a constant price

At the last in-lab Experimental Tobacco Marketplace session participants may be recruited for an addendum to this study, which includes two additional sessions (described below). If the participant agrees and is a female, she may be retested for pregnancy at this time. Participants will only be approached and recruited contingent upon approval by the FDA Center for Tobacco Products for these additional sessions.

Post-marketplace Sampling (1 session; approximately 15-30 minutes): After at least approximately five days following the fourth marketplace session, participants may return to the laboratory for the ability to return any unused experimenter provided products for a refund and report the number of tobacco products used since the previous session. During this session, all participants, regardless of assigned investigational cigarette concentration, will be provided five-days' worth each of the "high" (17.4 mg/g) and "low" (0.4 mg/g) investigational cigarette. In addition to the "Investigational Tobacco Product" label, these cigarettes will be labeled with arbitrary codes e.g., "A" and "B" (randomized across participants as to which concentration the code reflects); for subsequent tasks, participants will be told that cigarette "C" refers to the investigational cigarette they were assigned to at the onset of the study. Participants will be told to use only these cigarettes for the following five days.

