cigarettes, usual brand of cigarettes, and other nicotine products will all be available, mimicking a regulatory environment where reduced-nicotine cigarettes are made available in the marketplace, but conventional cigarettes remain available as well. This condition will include double the pricing scenarios such that both reduced-nicotine and conventional cigarettes will alternately serve as the modified-price and constant-price commodity, allowing us to measure symmetrical cross price elasticity for conventional and reduced-nicotine cigarettes (**Table 2**). Participants will be compensated \$20 for the consent session, \$40 for the assessment session, \$20 for each of the four Experimental Tobacco Marketplace sessions, \$20 in experimental income to be kept and/or used for tobacco/nicotine products in the Experimental Tobacco Marketplace sessions, and \$75 for completing all sessions for a maximum total of \$295.

Sample Size Justification

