For Aim 2, we request a total sample size of n=150 completed participants (30 per dose). The goal of Aim 2 is to analyze condition effects within each dose. To estimate an effect size for this experiment, the same paper (Johnson, et al., 2004) used in Aim 1 was used to estimate the effect of introducing reduced-nicotine cigarettes into a condition containing conventional cigarettes and an alternate commodity (nicotine gum in the previous paper), one of the main analysis types we intend to do (see below). In this paper, using a reanalysis similar to that described above, making denicotinized cigarettes available in addition to conventional cigarettes and gum reduced the substitution of nicotine gum, which was associated with an effect size of $f = 0.382$, which is near to a 'large' effect by convention (Cohen, 1992). Due to the multifaceted nature of the analyses in Aim 2, we chose a more conservative effect size of $f = 0.25$, a 'medium' effect. Using this effect size, our power analysis yielding 30 participants per dose based on a within-factors ANOVA for each individual dose, 4 repeated measures (conditions), a type 1 error rate of $\alpha = 0.05$, and 90% statistical power. Further, our tests include the statistical interaction between dose and scenario using a within-between interaction ANOVA model. With the requested sample size, we will have sufficient statistical power to detect interaction effects of $f = 0.14$, close to a 'small' effect size. Hence, we have ample statistical power to detect meaningful effects in this study. These analyses were performed in G*power version 3.1.9.2.

Data Analyses

General Demand Analysis Procedure. The nonlinear regression demand analyses to obtain subject-specific measures of intensity and elasticity are analogous to Aim 1. To satisfy the goals of Aim 2, data will be further analyzed as described below.

General Substitution Analyses Procedure. Aim 2 involves a number of comparisons of substitution among products in the four scenarios in addition to the demand-style analyses in Aim 1. To address the substitution goals we will use a modification analogous to that we've used before (Koffarnus, et al., 2015) of an equation proposed by Hursh and Roma (2013), which relates consumption of a fixed-price commodity (e.g., a non-combustible nicotine product in condition **a** of **Table 2**) as price of a primary commodity (e.g., usual brand of cigarettes in condition **a**) changes:

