$$Q = Q_{alone} * 10^{I * e^{-\beta C}}$$

In this equation, Q_{alone} represents the maximum consumption of the fixed-price commodity when the primary commodity has a price high enough to drive consumption to zero, β is the sensitivity of fixed-price commodity consumption to the price of the primary commodity, I is an interaction parameter that indicates whether the fixed-price commodity is a substitute (positive I value), complement (negative I value), or independent (I value near zero), and Q and C represent consumption of the fixed-price commodity and cost of the primary commodity, respectively, and are known from data. This equation has three parameters (Q_{alone} , I , and β) that will be estimated from experimental data using nonlinear regression. Analysis will proceed similarly as in Aim 1 with the substitution equation being fit to individual subject data to generate subject-specific estimates of maximum consumption, interaction, and sensitivity. These values will then be further analyzed to satisfy the goals of Aim 2.

Primary Analyses of Interest in Aim 2. Aim 2 involves a number of comparisons between demand characteristics (intensity and elasticity) and substitution (maximum consumption, sensitivity, interaction) across and within both doses and conditions involving three types of commodities (reduced-nicotine cigarettes, conventional cigarettes, and other non-combustible products). Within-dose statistical comparisons are briefly described in **Table 2**. Each of these effects will also be compared in larger mixed-effect models across dose with dose entered as a between-subject variable to determine the degree to which these substitution and demand effects differ by dose.

1. Compare substitution (maximum consumption, sensitivity, and interaction) of conventional cigarettes for reduced-nicotine cigarettes and vice versa in condition **d**. In separate pricing scenarios, this condition will include both conventional and reduced-nicotine cigarettes as a constant-price and modified-price commodity, allowing us to assess the degree to which the two cigarette types substitutes for one another. This analysis will inform regulators the degree to which reduced-nicotine cigarettes will, at each of the doses included here, replace conventional cigarettes in the marketplace as a functionally equivalent commodity (substitutes) or act independently in the marketplace without affecting consumption of the other cigarette (independents).

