2. This analysis will compare demand intensity and elasticity of reduced-nicotine cigarettes across conditions **b**, **c**, and **d**, informing regulators of the degree to which consumption of reduced-nicotine cigarettes at each of the doses studied here changes as a function of the other nicotine products present in the marketplace, including conventional cigarettes.
3. This analysis is analogous to analysis 2, but will compare demand intensity and elasticity of conventional cigarettes across conditions **a** and **d**, informing regulators of the degree to which consumption of conventional cigarettes is affected by the presence or absence of reduced-nicotine cigarettes in the marketplace at each reduced-nicotine dose.
4. This analysis will also compare whether cross-price elasticity parameters (maximum consumption, sensitivity, and interaction) for non-combustible products change when reduced-nicotine cigarettes are added to the current marketplace in addition to conventional cigarettes (**a** versus **d**), and when reduced-nicotine cigarettes replace conventional cigarettes in the marketplace (**a** versus **c**). These analyses will inform regulators how the introduction of reduced-nicotine cigarettes at each dose included here will affect the overall nicotine product marketplace and influence consumption of other nicotine products.
5. This analysis will compare substitution of other nicotine products for reduced-nicotine cigarettes with (condition **d**) and without (condition **c**) conventional cigarettes in the marketplace. This analysis will inform regulators how, under circumstances where reduced-nicotine cigarettes are present in the marketplace at one of the doses studied here, removal of conventional cigarettes will affect consumption of other nicotine products also present in the marketplace.

To complete the analyses in Aim 2, a random effect will be included to model any subject effect, and socio-economic and other demographic variables will be statistically screened for inclusion using model-based hypothesis tests.

Difficulties and Limitations

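### Aim 2's 90% power is for a four-condition within-dose ANOVA, but no listed primary analysis compares four conditions; at the same f, power is about 84% (three levels) or 75% (two levels), depending on an unstated correlation

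*Combined protocol and SAP*

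**What the plan says.** The Sample Size Justification for Experiment 2 says that Aim 2 concerns condition effects within each dose. It asks for 150 completers, 30 in each of five dose groups. The power calculation is "based on a within-factors ANOVA for each individual dose, 4 repeated measures (conditions"), with f = 0.25, alpha = 0.05 and 90% power, run in G*Power 3.1.9.2. No correlation among repeated measures and no nonsphericity value is given. The value 0.25 was chosen as a cautious step down from f = 0.382, the effect found in a reanalysis of an earlier three-product study. The paragraph concludes that power is ample.

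The section on primary analyses of interest in Aim 2 then lists five analyses:

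- **Analysis 1:** substitution of conventional for reduced-nicotine cigarettes and the reverse, both within condition d. Of condition d the plan says "This condition will include double the pricing scenarios".
- **Analysis 2:** "demand intensity and elasticity of reduced-nicotine cigarettes across conditions b, c, and d".
- **Analysis 3:** "demand intensity and elasticity of conventional cigarettes across conditions a and d".
- **Analysis 4:** cross-price parameters for non-combustible products, a versus d, and also "when reduced-nicotine cigarettes replace conventional cigarettes in the marketplace (a versus c").
- **Analysis 5:** substitution of other products for "reduced-nicotine cigarettes with (condition d) and without (condition c) conventional cigarettes".

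The same section adds: "Within-dose statistical comparisons are briefly described in Table 2". That table is not in the text available for this review.

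**The concern.** The sample size rests on a test with four repeated levels, and the listed analyses have three levels at most. This is not loose wording in the list, because it follows from the design. In section 5.1 of the Experiment 2 application, the second marketplace condition reads "Price of experimental cigarettes will be manipulated with no other products available", so other products are absent there. Conventional cigarettes are absent from the second and third conditions, and experimental cigarettes from the first. No single product is on sale in all four.

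At a fixed f and n, a repeated-measures test on fewer levels has less power. If the plan's f is meant to apply to the listed analyses, the chance of missing such an effect in a two-level test is nearer one in four than one in ten. That matters for null results. The plan intends to tell regulators whether products act independently of one another, and whether conventional-cigarette demand changes when reduced-nicotine cigarettes are on sale. A reader who believes power was 90% would put too much weight on a finding of no effect.

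**Working it through.** **Inputs.** From the Sample Size Justification: n = 30 per dose, f = 0.25, alpha = 0.05, m = 4 levels. From the list of primary analyses: m = 3 for analysis 2; m = 2 for analyses 1, 3, 4 and 5. Assumed because unstated: correlation rho, and nonsphericity epsilon = 1 unless noted.

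**Formula** (one-group within-factors ANOVA, noncentral F):

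- lambda = n × m × f² × epsilon / (1 − rho)
- df1 = (m − 1) × epsilon; df2 = (n − 1)(m − 1) × epsilon
- power = probability that a noncentral F(df1, df2, lambda) exceeds the 5% critical value

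**Step 1: reproduce the plan.** With m = 4 and rho = 0.5, lambda = 30 × 4 × 0.0625 / 0.5 = 15, df = 3 and 87, and power is 90.4%. At n = 29 it is 89.2%. So 30 is the smallest n reaching 90%. On a 0.01 grid with epsilon = 1, only rho = 0.50 and 0.51 give that result (0.49 needs 31; 0.52 needs 29), so 0.5 appears to be the value used.

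**Step 2: the listed analyses, same inputs.**

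- Three levels: lambda = 30 × 3 × 0.0625 / 0.5 = 11.25, df = 2 and 58, power 84.1%.
- Two levels: lambda = 30 × 2 × 0.0625 / 0.5 = 7.5, df = 1 and 29, power 75.4%. A paired t-test with standardised difference 0.5 gives the same figure.

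**Step 3: range over rho** (n = 30, f = 0.25, epsilon = 1).

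| rho | 4 levels | 3 levels | 2 levels |
|---|---|---|---|
| 0.4 | 83.9% | 76.6% | 67.6% |
| 0.5 | 90.4% | 84.1% | 75.4% |
| 0.6 | 95.8% | 91.5% | 84.1% |
| 0.7 | 99.1% | 97.3% | 92.7% |

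To reach 90% with 30 per dose, rho must be at least about 0.58 for three levels or 0.67 for two.

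**Step 4: detectable f at 90% power.** At rho = 0.5 it is 0.272 (three levels) and 0.306 (two levels). Over rho 0.4 to 0.7 it runs from 0.298 to 0.211, and from 0.335 to 0.237.

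**Step 5: nonsphericity.** With epsilon = 0.75 and rho = 0.5, three-level power falls to 75.6%. Two-level tests do not depend on epsilon.

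**Step 6: larger effects.** At f = 0.382 and rho = 0.5, power is 99.6% (three levels) and 98.1% (two levels). Over rho 0.4 to 0.7, two-level power is 95.8–99.9% and three-level power is at least 98.8%.

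**Step 7: what f = 0.25 over four means implies for a pair.** The largest standardised difference lies between 2f = 0.50 and f × √8 = 0.707. The two-level f is half of that, 0.25 to 0.354, with power 75.4% to 96.3% at rho = 0.5. Pairs other than the largest can have less.

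**The case against.** The strongest reply is that nothing in the plan is miscalculated and that 75% is a pessimistic reading. Cohen's f is not fixed across numbers of levels: four evenly spaced means with f = 0.25 give an extreme pair with two-level f of about 0.335 and power of about 94% at rho = 0.5. The plan's only empirical effect, f = 0.382, comes from adding denicotinized cigarettes to a market with conventional cigarettes and gum. That is essentially the a-versus-d contrast of analysis 4, and power there is 98%. On that evidence the plan's confidence is defensible.

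Much of this stands, and it limits the point to effects near f = 0.25. It does not remove it. The plan deliberately set its power at 0.25 because of the range of analyses, so the figure quoted at that value should describe those analyses. The 94% applies only to the most separated pair, and the plan does not say which pair that would be.

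A second reply is that rho = 0.5 was inferred with epsilon = 1. Other pairs also make 30 the smallest n at four levels: epsilon 0.9 with rho 0.54, 0.75 with 0.60, and 0.6 with 0.66. Two-level power is then 79%, 84% and 89%. That is a fair correction to how firmly 75% can be held, but every one of these is still below 90%, and three-level power stays near 84%.

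Third, Table 2 is not available, matching the numbered conditions in section 5.1 to letters a to d is an inference, and some level counts involve judgement. Analysis 4 could be run as one a/c/d test, and analysis 1 also asks about the sign of the interaction parameter. None of these yields four levels. A four-level outcome could be constructed, such as demand for whichever cigarette has its price varied, but none is listed. Finally, the mixed models across dose use all 150 participants, but they supplement the within-dose tests rather than replace them.

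**Conclusion.** The concern holds. The plan's 90% is correctly computed for a four-level within-dose test, but that test is not among the listed primary analyses. At f = 0.25, n = 30, alpha = 0.05, rho = 0.5 and epsilon = 1, power is about 84% for analysis 2 and about 75% for analyses 1, 3, 4 and 5. For the latter four the type II error is about 25%, with a range of 7% to 32% for rho from 0.7 to 0.4, where the plan implies 10%. These figures assume that the same f applies at each number of levels and include no multiplicity adjustment. At f = 0.382 power remains high, so the design is not shown to be inadequate; its stated operating characteristic is attached to the wrong test. This should be fixed, but it does not call for a larger trial.

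**What to change.** Keep 30 per dose. In the Sample Size Justification for Experiment 2, replace the single 90% figure with power or detectable f for each listed analysis, and state rho and epsilon with a range over rho. Suitable wording would be:

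*At f = 0.25, alpha = 0.05, 30 per dose, rho = 0.5 and epsilon = 1, power is about 84% for analysis 2 (77–97% for rho 0.4–0.7) and about 75% for analyses 1, 3, 4 and 5 (68–93%). Detectable f at 90% power is 0.27 and 0.31 respectively. At f = 0.382, power is 98% or more at rho = 0.5.*

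Add that f is taken as the same at each number of levels, and qualify the statement that power is ample. If a four-condition outcome is intended, define it and add it to the list of primary analyses.

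As a separate clarification, give the power level and number of levels behind the detectable interaction of f = 0.14. With N = 150, rho = 0.5 and epsilon = 1, power at that value is 91.7%, 86.0% and 77.8% for four, three and two levels.

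The cost is the wording of one paragraph and a less favourable power statement at f = 0.25. No participants are added and study conduct does not change.
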